**Exploratory Aim.** To evaluate the effect of varenicline on negative affect, and the relationship between negative affect and cannabis use reduction, during CUD treatment. **Exploratory Hypothesis 1:** A 12-week treatment course of varenicline, compared to placebo, for CUD will yield reduction in negative affect. **Exploratory Hypothesis 2:** Reduction in negative affect during varenicline treatment will be associated with cannabis use reduction.

**Participants.** A total of approximately180 participants with CUD, aged 18 and over, will be recruited over a 32-month period at 2 participating sites.

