**Exploratory Analysis.** **Exploratory Aim 1:** Negative affect will be measured weekly during study treatment and compared between groups using generalized linear mixed effects regression models. Model based means will be used to construct the pairwise comparisons between groups and treatment by time interactions will be included to assess differential response over time. **Exploratory Aim 2:** Further, we will assess the time varying relationship between changes in negative affect and cannabis use sessions. Cross lagged panel models will be used to assess the lagged effect of changes in negative affect on cannabis use and visa-versa. Models will also include the autoregressive and synchronous relationships between these variables over time. Models will evaluate the influence of study treatment and medication adherence on the relationship between negative affect and cannabis use through the inclusion of time variable and time invariate effects. If significant treatment effects exist, additional stratified analysis will be conducted to elucidate the magnitude and direction of the effect.

**Additional Data Analysis.** Logistic regression models will be used to assess end of study abstinence (7 day point prevalence abstinence at week 12 and continuous abstinence from week 6 to 12); primary analysis models will be reported both as design adjusted results as well as adjusted for significant clinical covariates. To comprehensively examine the longitudinal efficacy of varenicline, weekly cannabis abstinence will also be analyzed over the entire treatment course using generalized linear mixed effects regression models under a GEE framework. Between study visit cannabis use will be based on daily substance use diaries confirmed via Time-Line Follow-Back procedures. The number of treatment visits attended will be compared between groups using Poisson regression models, while the number of days retained will be assessed using Cox Proportional Hazards regression models. Medication adherence (REDCap video capture of medication-taking; pill counts), tobacco smoking status, and gender will be explored as potential moderators of study outcomes through model interactions. Craving and withdrawal from cannabis will be assessed between groups over time using generalized linear mixed effects models.

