substance use report logs. We anticipate the increased information will allow better precision in the estimated effect between randomized study groups. Assuming this, coupled with the more extended 12-week treatment compared with the truncated treatment phase in the prior UG3 proof-of-concept trial, results in a slightly increased effect size of  $d=0.5$ , a high correlation between measures taken over time on the same participant ( $p=0.95$ ) and a 5% type 1 error rate, 57 participants are necessary in each treatment arm to achieve adequate power (80%). Additionally, the UG3 noted a higher than expected attrition rate of 35%, thus we anticipate that, despite our best efforts and revised approach, attrition during the study could reach 35%. Thus to ensure that we have the appropriate sample, we will enroll and randomize **approximately 90 participants per group for a total sample size of approximately n=180**. This will allow us to detect a difference in cannabis use session of at *least*  $d=0.5$  between randomized study groups while accounting for up to 35% study attrition. Similar to adult varenicline phase III studies (Gonzales et al., 2006), for the primary safety analysis we will compare the frequency of all treatment-emergent AEs (defined as any AE occurring between treatment initiation and one week following treatment conclusion), SAE's between varenicline and placebo groups. A non-inferiority analysis will be utilized (Piaggio et al., 2006). With an estimated placebo treatment-emergent AE rate of 75% (Gonzales et al., 2006), 90% power and two sided  $\alpha = 0.05$ , within our proposed sample of **approximately 180 randomized participants** we will be able to detect a 10% non-inferiority margin in AE frequency between treatment groups if it exists.

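### Exploratory Aim 2 names no term that separates stable differences between people from change within a person, so its lagged paths can be significant, in either direction, when no lagged effect exists

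*Combined protocol and SAP*

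**What the plan says.** The Exploratory Analysis part of Statistical Analysis gives the purpose: "we will assess the time varying relationship between changes in negative affect and cannabis use sessions". The method follows: "Cross lagged panel models will be used to assess the lagged effect of changes in negative affect on cannabis use and visa-versa". Two more sentences complete the model: "Models will also include the autoregressive and synchronous relationships between these variables over time"; and the influence of treatment and adherence on the relationship is to be evaluated "through the inclusion of time variable and time invariate effects". Last comes a conditional step: "If significant treatment effects exist, additional stratified analysis will be conducted to elucidate the magnitude and direction of the effect".

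The hypothesis that this serves is Exploratory Hypothesis 2 (Study Overview and Design): "Reduction in negative affect during varenicline treatment will be associated with cannabis use reduction".

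Three things are left open:

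- No random intercept, person-mean centring or fixed person effect is named.
- The text speaks of changes in affect without saying whether levels or change scores enter the model.
- The section states "Negative affect will be measured weekly during study treatment" but names no scale for it. PROMIS-29, whose description covers anxiety and depression, has four marks in the schedule of assessments (Table 6).

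No sample size, power or error rate is given for this aim.

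**The concern.** The question is about order within a person: does a shift in affect precede a shift in use, or the reverse? A cross-lagged model on levels controls for the previous value of use, but one lagged value is an imperfect measure of a person's usual level. What it misses stays in the residual. If people whose affect is usually worse also usually use more, lagged affect picks up that remainder and is given a lagged path. The same happens from use to affect, which the plan also tests.

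At stake is the reading of Aim 2: a cross-sectional link between people could be reported as a temporal effect. The primary analysis and Exploratory Aim 1 are both specified as mixed effects models. Aim 2, where the separation matters most, has no such term.

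**Working it through.** **The plan's only efficacy sample-size figure.** Power and Sample Size assumes "a high correlation between measures taken over time on the same participant" of 0.95, d = 0.5, 5% error (two-sided assumed) and 80% power, and reaches 57 per arm.

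- Single measure: n = 2(1.9600 + 0.8416)²/0.5² = 62.79.
- Mean of 7 weekly values (weeks 6 to 12), AR(1) at 0.95: variance factor 0.8926, so 62.79 × 0.8926 = 56.05, rounded up to 57. This matches.
- Exchangeable at 0.95 (a stable trait): factor (1 + 6 × 0.95)/7 = 0.9571, so 60.1, rounded up to 61. This does not match.
- Attrition: 57/0.65 = 87.7, in line with about 90. Conversely, 180 × 0.65 = 117 completers.

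So the 0.95 concerns cannabis use only, and the structure that reproduces 57 is one without stable traits.

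**Spurious path expected with no lagged effect.** Let s_A and s_U be the stable shares of variance for affect and use, r the correlation of the stable levels, and w the same-week correlation of the deviations, with deviations independent from week to week. All are assumptions. Put c = r√(s_A·s_U) and c₀ = c + w√((1 − s_A)(1 − s_U)). Then

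affect-to-use path = (c − c₀·s_U)/(1 − c₀²); for use-to-affect replace s_U by s_A.

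- s = 0.6 for both, r = 0.3, w = 0: 0.18 × 0.4/(1 − 0.18²) = 0.074.
- s = 0.6, r = 0.3, w = 0.2: c₀ = 0.26, (0.18 − 0.156)/(1 − 0.26²) = 0.026.
- s = 0.6, r = 0.2, w = 0.2: c₀ = 0.20, (0.12 − 0.12)/(1 − 0.20²) = 0.
- s = 0.6, r = 0, w = 0.2: c₀ = 0.08, (0 − 0.048)/(1 − 0.08²) = −0.048.

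The artefact can therefore be positive, absent or negative.

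**Simulated false-positive rates, affect-to-use, n = 117** (Gaussian data, pooled lagged regression, two-sided 5%, 1000 runs, s = 0.6 for both, independent deviations):

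| r | w | 4 waves | 13 waves |
|---|---|---|---|
| 0 | 0 | 3% | 11% |
| 0.2 | 0 | 21% | 61% |
| 0.3 | 0 | 40% | 88% |
| 0.5 | 0 | 84% | 100% |
| 0.3 | 0.2 | 9% | 28% |
| 0.5 | 0.2 | 46% | 91% |

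The 11% in the first row has no biased path behind it. It comes from model-based standard errors that ignore the remaining within-person correlation.

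With autocorrelation 0.3 in the deviations the rates are lower. At n = 117 and r = 0.4 they are 48% (4 waves) and 94% (12 waves) with w = 0, and 13% and 43% with w = 0.2. Over r = 0.2 to 0.4, w = 0 or 0.2 and n = 117 to 180, the range is about 3% to 63% with 4 waves and about 4% to 99% with 12.

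**Use very stable (s_U = 0.95, s_A = 0.6).** With r = 0.3 and w = 0, c = 0.3√0.57 = 0.2265. Affect-to-use is 0.2265 × 0.05/(1 − 0.2265²) = 0.012; use-to-affect is 0.2265 × 0.40/(1 − 0.2265²) = 0.096. Across r = 0.3 and 0.5 and w = 0 and 0.2 at n = 117, the use-to-affect path is falsely significant in 46% to 97% of 4-wave trials; the affect-to-use path in 4% to 17%.

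**No stable traits (AR(1)), n = 117.** The model holds its level: 4.4% with 4 waves, 4.7% with 13.

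**Change scores as predictor.** Stable levels cancel: about 6% to 11% with w = 0. With w = 0.2 a negative path appears instead, significant in 18% to 36% of 4-wave trials at n = 117.

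**Random-intercept model, 4 waves, 300 runs, likelihood-ratio test** (s = 0.6 for both, independent deviations):

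| n | r, w | Standard model | Random intercepts |
|---|---|---|---|
| 117 | 0.5, 0.2 | 41% | 6.0% |
| 117 | 0.3, 0 | 38% | 7.3% |
| 180 | 0.5, 0.2 | 63% | 4.0% |
| 180 | 0.3, 0 | 56% | 6.0% |

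The Monte Carlo standard error around 5% is √(0.05 × 0.95/300) = 1.3 points. The standard-model rates at n = 117 differ from the first table only by simulation error. None of the simulations uses counts, missing data, a treatment effect or paths that vary over time.

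**The case against.** - **Silence is not a choice.** The text neither specifies nor excludes random intercepts. That stands: the defect is under-specification, though the listed paths read most plainly as a standard model.
- **The inputs are assumed.** That also stands. The high rates need correlated stable levels, little same-week correlation and, for those near 99%, 12 waves of affect data, whereas PROMIS-29 shows four marks.
- **The 0.95 correlation.** A reader might infer that the plan itself assumes very stable differences between people. The documents do not support this: the figure concerns use alone, no structure is stated, and 57 per arm follows from AR(1). It should not be cited in support.
- **Change scores.** If these are meant, the mechanism above largely drops out, but another artefact can replace it. The plan has to say which is meant.
- **Treatment arms.** A reader might infer that a pooled path will stand in for the varenicline relationship unless a treatment effect is significant. The plan evaluates the influence of treatment on the relationship without condition; only the further stratified analysis depends on significance.
- **The remedy is lightly tested.** It was fitted with 4 waves as a single group, not as a two-group model with about 58 completers per arm (90 × 0.65 = 58.5).

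**Conclusion.** The point holds as an inexpensive improvement to an exploratory analysis. As written, Aim 2 names no safeguard against stable differences between people appearing as lagged effects. At a stable share of 0.6 and trait correlations of 0.2 to 0.4, the affect-to-use error rate runs from about nominal to many times 5%, and more waves make it worse. Those inputs are assumptions, not figures from the documents. If use is very stable, the use-to-affect path is the one chiefly at risk. With no stable traits the standard model holds about 5%.

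A reader might go further and conclude that the trial will report that mood change drives cannabis use. The documents do not support that: the hypothesis is worded as an association, the model is not fully specified, and the artefact can vanish or change sign. The primary efficacy and safety analyses do not use this model.

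**What to change.** In the Exploratory Analysis text:

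1. Name a random-intercept cross-lagged panel model as the main Aim 2 model, keeping the planned synchronous paths and the treatment and adherence effects.
2. State that levels, not change scores, are modelled.
3. Report the standard model only as a secondary result, read as association.
4. Report the treatment difference in the affect-to-use path with its CI, whatever its significance. A full two-group model is optional.
5. Name the negative-affect scale and reconcile weekly measurement with the four PROMIS-29 marks in the schedule. This settles the number of waves and the length of the lag.
6. Name a fallback for non-convergence, such as a mixed model with the lagged predictor split into person mean and within-person deviation.

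The cost is SAP wording and modest programming. Intervals will be wider, because only within-person change informs the paths, and convergence problems are possible.

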Treatment Assignment. Individuals who meet all inclusion criteria and no exclusion criteria will be randomized to receive either varenicline or matching placebo. Randomization (stratified on tobacco smoking status and gender) and dispensing will be performed by the MUSC Investigational Drug Service. Varenicline will be provided at the standard recommended dose of 0.5mg daily for three days, then 0.5mg twice daily for four days, and then 1mg twice daily for the remainder of the 12-week treatment period. Matching placebo and varenicline (0.5mg and 1mg) capsules will be compounded by IDS utilizing Letco 00 capsules and microcrystalline cellulose filler. For the Pickens site, medication will be packaged and dispensed by MUSC IDS, and then shipped to Pickens via registered courier. On site, medication will be stored in a controlled access environment and provided to participants by appropriately trained and designated study staff, with double checks in place. In extenuating or emergency circumstances, when patient visits are not feasible or are prohibited, such as in the case of a pandemic, weekly medication may be mailed to participants.

Medication Management. Medication Management (MM) is a common-sense, generalizable approach to encourage adherence to medication specifically, and to a treatment plan in general. Once a week, participants will be seen for a brief MM session. Sessions will be focused on (a) developing and maintaining rapport, (b) reviewing AEs and concomitant medications, and (c) discussing progress with medication adherence and cannabis reduction/abstinence. These sessions provide an opportunity to address challenges and help participants devise strategies for success. A similar intervention was utilized in the NIDA-funded CTN0053 trial (Achieving Cannabis Cessation—Evaluating N-Acetylcysteine Treatment) to provide an evidence-based treatment platform for all participants. MM with participants at the Pickens site will be done by approved medical personnel there and, as needed, by MUSC site medical personnel via WebEx or Doxy.me, HIPAA-compliant, MUSC Information Security-approved platforms for telehealth. In extenuating or emergency circumstances, when patient visits are not feasible, safe, or are prohibited, such as in the case of a pandemic, MM at both sites may be completed remotely by telehealth/phone.

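### Visits attended, a count capped at 12 and shaped by dropout, is compared by Poisson regression with no variance correction, so its error rate is generally not the nominal 5%

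*Combined protocol and SAP*

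**What the plan says.** The sentence at issue, under Additional Data Analysis in Statistical Analysis, is: "The number of treatment visits attended will be compared between groups using Poisson regression models". The same sentence goes on to name a Cox model for time retained. No dispersion check, robust variance or bounded-count model is named for the visit count.

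The cap follows from Procedures. On visit frequency: "Once a week, participants will be seen for a brief MM session". On treatment length, the dosing text runs: "1mg twice daily for the remainder of the 12-week treatment period". One visit a week for 12 weeks gives a count from 0 to 12, which agrees with the week 1 to week 12 columns of the schedule of assessments.

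Power and Sample Size gives the trial size, "approximately 90 participants per group for a total sample size of approximately n=180", and warns that "attrition during the study could reach 35" percent.

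A switch to a negative binomial model when overdispersion is detected appears in the Specific Aim 1 text. The surrounding sentences concern use sessions: the offset for visit timing, the working correlation and the adjustment for baseline use.

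**The concern.** Poisson regression with its usual standard errors assumes that the variance equals the mean. Visits attended will not look like that. Completers pile up near 12 and dropouts lie anywhere below, so the variance is set by how many leave and when. Early dropout makes it larger than the mean, and the test then finds false differences too often. Late or infrequent dropout makes it smaller, and the test then has almost no false positives but loses power to see a real difference.

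The comparison matters because attrition may be substantial, and whether the arms differ in attendance is part of how the weeks 6-12 efficacy result will be read.

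**Working it through.** **Inputs from the documents.** Weekly visits over 12 weeks; about 90 per arm; attrition of up to 35%.

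**Assumptions, not in the documents.** Timing of dropout; 95% attendance at each visit while retained; a two-sided 5% test, since the plan assigns no alpha to this comparison; the same distribution in both arms (the null).

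**Step 1, the plan's own figure.** The plan gives no figure for visits attended. Its sample size is 57 evaluable per arm inflated for 35% attrition: 57 / (1 - 0.35) = 87.7, so 88, which agrees with about 90.

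**Step 2, variance-to-mean ratio.** Let K be the last week in the study (12 for completers) and p = 0.95, with visits attended binomial(K, p). Then

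- mean = p E(K)
- variance = p(1 - p) E(K) + p² Var(K)
- φ = variance / mean = (1 - p) + p Var(K) / E(K)

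**Step 3, actual error rate.** The Poisson standard error of the log ratio of the arm totals is sqrt(1/S_A + 1/S_B). The true variance is φ times the square of that, so the type I error is 2[1 - Φ(1.96/√φ)].

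**Three worked cases at 35% attrition.** Completers contribute 0.65 × 12 = 7.8 to E(K) and 0.65 × 144 = 93.6 to E(K²).

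- *Dropouts' last visit uniform on 0-11.* E(K) = 7.8 + 0.35 × 5.5 = 9.725. E(K²) = 93.6 + 0.35 × 42.167 = 108.36. Var(K) = 108.36 - 94.58 = 13.78. φ = 0.05 + 0.95 × 13.78/9.725 = 1.40. Error = 9.7%.
- *Last visit uniform on 0-4.* E(K) = 7.8 + 0.35 × 2 = 8.5. E(K²) = 93.6 + 0.35 × 6 = 95.7. Var(K) = 95.7 - 72.25 = 23.45. φ = 0.05 + 0.95 × 23.45/8.5 = 2.67. Error = 23%.
- *Last visit uniform on 8-11.* E(K) = 7.8 + 0.35 × 9.5 = 11.125. E(K²) = 93.6 + 0.35 × 91.5 = 125.63. Var(K) = 125.63 - 123.77 = 1.86. φ = 0.05 + 0.95 × 1.86/11.125 = 0.21. Error is about 0%.

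**All patterns, same formula.**

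| Attrition | Dropout pattern | φ | Type I error |
|---|---|---|---|
| 35% | Constant hazard | 1.54 | 11.5% |
| 35% | Uniform, last visit 0-11 | 1.40 | 9.7% |
| 35% | Uniform, last visit 1-11 | 1.17 | 7.0% |
| 35% | Last visit 0-4 | 2.67 | 23% |
| 35% | Last visit 1-4 | 2.35 | 20% |
| 35% | Last visit 8-11 | 0.21 | about 0% |
| 25% | Uniform, last visit 0-11 | 1.05 | 5.6% |
| 25% | Constant hazard | 1.12 | 6.4% |
| 20% | Uniform, last visit 0-11 | 0.86 | 3.5% |
| 20% | Constant hazard | 0.91 | 4.0% |
| 10% | Uniform, last visit 0-11 | 0.47 | 0.4% |

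Simulation of 20,000 null trials per pattern, 90 per arm, agrees with these to within half a percentage point.

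**Step 4, remedies.** In simulation, a variance estimated from the data (sandwich or quasi-Poisson) gives 4.4% to 5.4% in every pattern tried. A negative binomial model at 35% attrition gives about 0% to 5%: about 2.5-3% with a constant hazard, 1-2.5% when dropouts leave in roughly the first four weeks, and 0% with late dropout.

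**The case against.** Four points can fairly be made for the plan.

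1. *It does not say that model-based standard errors will be used, and the overdispersion rule could be read as general.* The first half is true, but model-based errors are the ordinary meaning of the words used. If the rule were carried over, the inflated figures would disappear. The test would then mostly be conservative, and underdispersion would remain untreated.

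2. *The 35% is a ceiling, and the timing is unknown.* This stands. If dropout is spread out and attrition is 20-25%, the Poisson test is close to nominal. That is a coincidence of the variance crossing the mean and cannot be relied on in advance.

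3. *The Cox model also addresses retention.* This stands. It needs no variance assumption about visit counts, so the visit comparison is not the only evidence on differential dropout. It does not repair the p-value for visits.

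4. *This is an additional analysis with no hypothesis or alpha attached.* This stands and sets the severity.

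A reader might infer that the error rate lies between 0% and 23%. It has no such bound: the same 35% gives about 25% if dropouts' last visit falls in weeks 0-3, and about 33% if they attend no treatment visit. A reader might also carry the earlier trial's 35% over six weeks forward to 12 weeks. That implies 1 - 0.65² = 58% attrition, beyond what this plan allows for.

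**Conclusion.** The analysis is wrong as written, at low severity. A count capped at 12 and governed by dropout does not have Poisson variance, and neither the sentence itself nor the Aim 1 overdispersion rule corrects for that. At the 35% ceiling the type I error is about 9-12% for spread-out dropout (7% if every dropout attends at least one visit), above 20% for dropout confined to the first four weeks, and near 0% for late dropout. At lower, spread-out attrition it is about 3-6% (20-25%) or about 0.4% (10%). All of these rest on assumed dropout timing and 95% attendance while retained.

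A reader might infer that false positives are to be expected, or that the efficacy result cannot be trusted because differential retention will be misjudged. The documents support neither. The direction of the error depends on timing that they do not give, retention is also analysed by the Cox model, the plan provides multiple imputation as a sensitivity analysis, and the primary efficacy and safety tests do not use this comparison.

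**What to change.** Keep the Poisson model for visits attended and state that inference will use a robust (sandwich) or quasi-likelihood variance. A binomial model for visits attended out of 12, with estimated dispersion, is an acceptable alternative. Extending the negative binomial rule to this outcome is not enough, because it does not restore 5% and cannot represent underdispersion. The cost is a phrase in the plan and one software option, with no effect on sample size or conduct.

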impact on parameter inference, thus when detected, a negative binomial distribution will be specified and model fit will be compared to the Poisson model. An offset variable will be included in the models to account for possible differences in between visit timing. Models will be computed both adjusted for design variables and for significant covariates and confounders found in the preliminary analysis. Working correlation structures will be independently compared using the quasi-likelihood under the independence model criterion statistic (QIC). Model based means will be used to construct the pairwise comparisons between groups. All design adjusted models will include baseline average use sessions, study visit, treatment group assignment and randomization stratification variables (smoking status and gender). Additional exploratory approaches (e.g., analysis excluding participants with <80% medication adherence, per protocol analysis, completers analysis) will be undertaken.

**Specific Aim 2:** We will also compare the frequency of treatment-emergent AEs between treatment groups using a non-inferiority analysis. Of particular interest will be AEs leading to medication discontinuation and the occurrence of treatment-related serious AEs (SAEs). We will specifically compare neuropsychiatric AEs and suicidality (C-SSRS) ratings by treatment group. We hypothesize that treatment with varenicline will not cause undue adverse events and will be non-inferior to the placebo group by a margin ( $\delta$ ) of no more than a 10% using the Farrington-Manning score test for non-inferiority.

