**Missing Data and Attrition.** Missing data in longitudinal studies can be a problematic feature but can be mitigated through study design considerations. In order to minimize missing data and study attrition, design simplification and enhanced communication between study staff and participants will be emphasized. We will make every effort to prevent attrition (e.g., phone/text visit reminders, participation compensation, reinforcing adherence to the study protocol). To assess the potential impact of missing data on the primary study hypothesis, sensitivity analysis will be completed (a) with all available data and (b) using methods of multiple imputation (Rubin, 1987). Multiple imputation will be implemented using fully conditional specification. Due to the possibly high rate of missing data near the end of the study treatment period (>10%), 100 imputation data files will be created to assure reasonable relative efficiency (Von Hippel, 2018).

**Power and Sample Size.** The proposed study is powered on the primary efficacy hypothesis that varenicline treatment, relative to placebo treatment, will yield reduced cannabis use during the crucial stages of study treatment (weeks 6-12). The UG3 portion of this study showed a moderate self-reported reduction of weekly use days between the varenicline and placebo group (Cohen's  $d=0.43$ ). We intend to improve the granularity of this measure by assessing, in more detail, the number of use sessions occurring on a daily basis using daily

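### Neither planned missing-data analysis of the primary outcome departs from missing-at-random, although the plan allows for up to 35% attrition

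*Combined protocol and SAP*

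**What the plan says.** The primary efficacy outcome is the weekly count of cannabis use sessions from daily logs, with main interest in weeks 6 to 12 (Statistical Analysis, Primary Analysis, Specific Aim 1). The Missing Data and Attrition paragraph lists measures to prevent dropout. It then says that, to assess the effect of missing data on the primary hypothesis, "sensitivity analysis will be completed (a) with all available data and (b) using methods of multiple imputation". It adds "Multiple imputation will be implemented using fully conditional specification" and "100 imputation data files will be created to assure reasonable relative efficiency", because late missingness may be high, possibly above 10%. The imputation variables and the assumed missing-data mechanism are not stated.

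Power and Sample Size reports 35% attrition in the UG3 trial and says that here "attrition during the study could reach 35" per cent.

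Other analyses that touch dropout are exploratory ("analysis excluding participants with <80% medication adherence, per protocol analysis, completers analysis") or compare retention between arms: visits attended by Poisson regression and days retained by Cox regression (Additional Data Analysis).

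**The concern.** Whether people who leave go on to use more or less cannabis than their recorded data predict, and whether that differs by arm, cannot be learned from the observed data. An analysis of available data and a standard imputation both fill this gap, implicitly or explicitly, with the same kind of assumption. If they agree, the reader learns that two methods sharing an assumption agree.

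The documents give a reason why leavers might differ by arm. Potential Risks cites relative risks on varenicline of 3.21 for nausea and 2.79 for abnormal dreams, and Specific Aim 2 singles out adverse events that lead to stopping medication. If such participants also leave the study, within-arm imputation would give them outcomes like those of people who stayed. Whether this will happen is unknown, and departures in the other direction are also possible. At stake is whether a reader of the final result can judge how far it rests on an untestable assumption.

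**Working it through.** **1. The plan's attrition figure.** 57 / (1 − 0.35) = 87.7, so 88 per arm, against the stated approximately 90. Retained: 90 × 0.65 = 58.5 per arm, above 57. The attrition step reproduces. (The 57 itself comes out at 61 by the standard formula with seven visits and correlation 0.95. Nothing here depends on it.)

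**2. What each planned analysis can show.**

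| Planned analysis | Varies the assumption about unseen use? |
|---|---|
| All available data | No. A likelihood mixed model needs missing-at-random; an unweighted marginal model generally needs more. |
| Fully conditional specification, 100 imputations | No. Standard form is valid under missing-at-random; no shift or reference-based step is stated. |
| Adherence-restricted, per-protocol, completers | No. They change the sample. |
| Visits attended, days retained | No. They compare dropout by arm, not use after dropout. |

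Adding craving, withdrawal and urine results to the imputation could make missing-at-random more plausible but would not test it. Remote daily logs, and the Time-Line Follow-Back also scheduled at FU 1, might recover some weeks. The documents do not say that either is collected after dropout.

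**3. Illustration of size.** From the plan: 90 per arm, d=0.5, correlation 0.95, 35% attrition, and baseline adjustment ("All design adjusted models will include baseline average use sessions"). Assumed: Gaussian outcomes, equal dropout in both arms, a two-sided 5% test, imputation from earlier weeks, and every shift. With early dropout all leavers go before week 6; with even accrual they leave throughout. In simulation the missing share of weeks 6–12 is 0.344 and 0.257 respectively.

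If varenicline leavers alone are δ SD worse than imputed, the effect is about d − share × δ. Significance is lost on average near δ = (d − 1.96 × SE) / share.

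- AR(1), early: SE 0.125, (0.5 − 0.245) / 0.344 = 0.74.
- AR(1), even: SE 0.116, (0.5 − 0.227) / 0.257 = 1.06.
- Exchangeable, SE about 0.04: (0.5 − 0.078) / 0.344 = 1.23 and 0.422 / 0.257 = 1.64.

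The shift itself adds variance, so simulated tipping points are lower: about 0.65 to 1.1 SD under AR(1) and 1.05 to 1.45 SD under exchangeable correlation.

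**4. Complete loss of benefit (δ = 0.5).** Early: 0.5 − 0.344 × 0.5 = 0.328. Even: 0.5 − 0.257 × 0.5 = 0.372. Simulation gave 0.323 and 0.374. The average result stays significant in both. Under AR(1) with early dropout, the share of significant trials falls from about 96% to 64%.

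**5. Other cases under AR(1).**
- With the UG3 effect, d=0.43 (measured on use days), tipping points at 35% attrition are 0.51 to 0.75 SD, and complete loss is 0.43 SD.
- At 10% attrition and d=0.5 they are 2.4 to 3.2 SD.
- A 0.5 SD shift in both arms leaves d at 0.50.
- The same shift in placebo leavers alone raises d to between 0.63 and 0.67, so missing-at-random would then be conservative.

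**6. Count scale.** Assume a mean of 20 sessions a week, 35% attrition and rate ratio = 1 − 0.5 × CV. Complete loss is then a multiplier of 1 / rate ratio. These rest on 60 to 80 replicates, so only one decimal is given for the tipping multiplier.

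| CV | Rate ratio | Complete-loss multiplier | Tipping multiplier |
|---|---|---|---|
| 0.4 | 0.80 | 1.25 | 1.4–1.5 |
| 0.6 | 0.70 | 1.43 | 1.6–2.0 |
| 0.8 | 0.60 | 1.67 | 2.0–2.4 |

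**The case against.** The strongest reply is that the illustration points towards robustness. In every set-up run, the tipping shift exceeds complete loss of the treatment benefit, so the average result turns only if varenicline leavers do worse than untreated. This stands, with two limits: it concerns averages, and early dropout with d=0.43 is close (0.51 against 0.43 SD).

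It also stands that the figures follow modelling choices. The plan gives a single correlation of 0.95 and no structure. AR(1) lets it decay with time, exchangeable does not, and the tipping points move accordingly. Leaving out baseline adjustment gives 0.42 to 0.61 SD, but the plan does adjust for baseline.

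Nor is 35% attrition the same as 35% missing outcome. It is a ceiling, and logs completed remotely could fill some weeks.

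Three stronger readings are tempting and are not supported:
- That missing-at-random overstates the effect. The documents give no data on use after dropout, and bias could run either way.
- That the plan contradicts itself. The Procedures section promises planned handling of missing data, and the plan does supply some. The gap is in what that handling can show.
- That the primary estimator is GEE, so the available-data analysis needs dropout completely at random. Specific Aim 1 names a mixed model but selects working correlations by QIC. The explicit GEE wording concerns weekly abstinence, a different outcome. That is a separate clarification; this point holds under either estimator.

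**Conclusion.** The gap is real: the plan sets out to assess the impact of missing data on its primary hypothesis, but nothing it lists varies the assumption on which that impact turns. The documents do not show that the result would be fragile. On the assumptions above, a one-arm departure larger than the whole treatment effect is needed to overturn the average result at 35% attrition, and at 10% the result is hard to overturn. A smaller departure still matters in an individual trial, as the fall from about 96% to 64% shows for one plausible set-up. A not-at-random analysis would therefore be informative. It should be added as an inexpensive improvement; its absence does not invalidate the design.

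**What to change.** Keep analyses (a) and (b), and list the imputation variables. Before unblinding, pre-specify one not-at-random sensitivity analysis on the 100 planned imputations: a delta-adjusted tipping point that multiplies the imputed weekly session counts after dropout.

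- Vary the multiplier separately by arm and in both directions.
- Include the case where varenicline leavers lose the whole benefit (multiplier equal to the reciprocal of the estimated rate ratio).
- Report the multiplier at which the conclusion changes, next to the retention comparison by arm.

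The cost is modest programming and a few sentences in the plan. Sample size, visits and participant burden do not change. The downside is that the reported result may look less robust than under the two current analyses alone.
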